8.4. Virology Assessments

Nasal swabs will be used to detect and/or quantify SARS-CoV-2. The presence of SARS-CoV-2 infection in nasal swabs will be assessed by the local laboratory (if feasible) and confirmed by the central laboratory using a PCR-based or other molecular diagnostic test.

Gene sequencing may be performed to detect changes in the S gene and potentially also other parts of the viral genome, if a sample is available.

Nasal swabs collected from adult participant or from neonates and infants (to be collected by qualified HCP only) with COVID-19-like symptoms will also be tested at the central laboratory for the presence of other respiratory pathogens using a broad respiratory pathogens panel (results may be shared with the site).

Adult participants, with stable/well-controlled HIV infection, will be encouraged to have HIV RNA viral load and CD4 cell count assessed at least twice a year and to provide these data for inclusion in the eCRF.

8.5. Genetics and Pharmacogenomics

Blood will be drawn at selected timepoints during the study for additional exploratory immunogenicity assessments, which may include limited genomic research (eg, RNAseq) .

8.6. Biomarkers

Blood will be drawn (PAXgene[®]) at selected timepoints during the study, as indicated in the Schedule of Activities.

For PAXgene[®] tubes collected in adult participants and in cord blood (if feasible), biomarker analysis may be performed to explore potentially informative biomarkers related to vaccine immunogenicity.

For adult participants with a positive test result for SARS-CoV-2 infection, biomarker analysis may be performed on PAXgene[®] tubes for evaluation of COVID-19 cases, and to explore potentially informative biomarkers correlated to SARS-CoV-2 infection and COVID-19 severity at Days 3 to 5, and at Day 29 (± 7 days) after onset of symptoms.

8.7. Medical Resource Utilization and Health Economics

Health Economics/Medical Resource Utilization and Health Economics parameters are not evaluated in this study.

9. STATISTICAL CONSIDERATIONS

Statistical analysis will be performed by the sponsor or under the authority of the sponsor. A general description of the statistical methods to be used to analyze the immunogenicity, safety and pregnancy outcomes data is outlined below. Specific details will be provided in the SAP.

9.1. Statistical Hypotheses

No formal statistical hypothesis is to be tested. The study is designed to provide descriptive information regarding the safety, pregnancy outcomes, and immunogenicity of Ad26.COV2.S in adult participants in the 2nd and/or 3rd trimester of pregnancy, as well as the safety and outcomes of neonates/infants. In addition, the study will provide descriptive information regarding the safety and immunogenicity of Ad26.COV2.S administered as a booster in eligible participants.

9.2. Sample Size Determination

The number of adult participants that will be assessed for safety and reactogenicity of the Ad26.COV2.S vaccine, was chosen to provide a preliminary assessment of safety and immunogenicity in this population.

A target of 240 adult participants in the 2nd or 3rd trimester of pregnancy, ≥ 18 to ≤ 45 years of age was planned to be enrolled in this study. As of Protocol Amendment 7 approval, participant enrollment in this study will be ceased.

Descriptive analysis will be used to evaluate the following:

- Safety and reactogenicity
- Pregnancy outcomes
- Neonate/infant outcomes
- Immunogenicity of Ad26.COV2.S in adult participants and neonates/infants (including immunity conferred by placental transfer of IgG antibodies).

When 40, 60, 120 and 240 participants are vaccinated, the observation of 0 AEs would be associated with a 95% confidence (2-sided) that the true rate is less than 8.8%, 6%, 3% and 1.5% respectively.

Table 3: Probability of Observing at Least One Adverse Event Given a True Adverse Event Rate

True Adverse Event Rate	Probability of Observing at Least One Adverse Event			
	N=40	N=60	N=120	N=240
0.5%	18%	26%	45%	70%
1.0%	33%	45%	70%	91%
1.5%	45%	60%	84%	97%
2.0%	55%	70%	91%	99%
2.5%	64%	78%	95%	>99%
3.0%	70%	84%	97%	>99%
5.0%	87%	95%	>99%	>99%
N: number of participants receiving study vaccine (Ad26.COV2.S).				

Subset of Participants for Th1/Th2 Assessments

The number of the subset of participants that was planned to be assessed for Th1/Th2 cellular immunogenicity of the Ad26.COV2.S vaccine, in participants from Week-16 of pregnancy through to delivery/termination, was chosen to provide a preliminary assessment of Th1/Th2 cellular immunogenicity in this population.

Table 4 provides the probabilities of observing at least one Th2 event given true Th2 rates.

Table 4: Probability of Observing at Least One Th2 Event Given a True Th2 Event

True Th2 Event Rate	Probability of Observing at Least One Th2 Event in N Participants Given a True Th2 Event
	N=25
0.5%	12%
1.0%	22%
2.5%	47%
5.0%	72%
10.0%	93%
25.0%	100%
50.0%	100%

The observation of 0 events is associated with 95% confidence (2-sided) that the true event rate is below the rates specified in Table 5 for the considered number of participants.

Table 5: Upper Limit of the 95% Two-sided Confidence Interval if no Cases are Observed for Different Sample Sizes

Sample Size	N=25	N=40	N=60	N=100	N=120	N=240
Upper Limit 95% two-sided confidence interval	13.7%	8.8%	6%	3.6%	3%	1.5%

9.2.1. Immunogenicity

Adults

The preliminary assessment of the average immunogenicity in the target population will be estimated with the 240 to be enrolled adult participants in the 2nd or 3rd trimester of pregnancy. No formal statistical hypothesis for immunogenicity will be tested. All immunogenicity analyses will be performed on the PPI-A by group (previous vaccination) and overall. Immunogenicity analyses may also be performed by stage of pregnancy (16-27 weeks, 28-38 weeks), administration of booster (Yes, No), SARS-CoV-2 baseline serostatus (Positive, Negative) at which the vaccine was administered and by vaccine history within each group.

The effect of homologous and heterologous boosters on binding antibodies and neutralizing antibody titers will be evaluated descriptively by group and overall.

One of the primary objectives of the study is to assess the humoral immune response in peripheral blood of adult participants induced by Ad26.COV2.S, administered intramuscularly (IM) as a

1-dose (5×10^{10} vp) schedule during the 2nd and/or 3rd trimester of pregnancy, with antibody levels and serological responses measured at 28 days after vaccination by ELISA (S-ELISA, EU/mL).

A secondary objective of this study is to assess the humoral immune response in peripheral blood of adult participants induced by Ad26.COVS administered IM as a 1-dose (5×10^{10} vp) schedule, during the 2nd and/or 3rd trimester of pregnancy, with serological responses (including antibody levels) measured at all blood collection timepoints by group and overall (including at the time of delivery [both peripheral blood and cord blood]), by ELISA (S-ELISA, EU/mL).

A further secondary objective is to assess the humoral immune response in peripheral blood of adult participants induced by Ad26.COVS administered IM as a 1-dose (5×10^{10} vp) schedule, during the 2nd and/or 3rd trimester of pregnancy, at all blood collection timepoints by group and overall, as measured by VNA titers (antibody GMTs), 28 days after vaccination (ie, on Day 29).

Serological response to vaccination as measured by binding (S-ELISA and/or equivalent assay) and neutralizing (VNA) antibody titers will be assessed to evaluate the humoral immune response in adult participants who receive a booster dose, pre-boost and at selected time points post booster vaccination by group and overall.

Neonates and Infants

No formal statistical hypothesis for immunogenicity will be tested. Immunogenicity analyses will be performed on the PPI-NVN set. Analyses may also be performed by vaccination regimen received by the infant's mother during pregnancy and the gestational age at the time of vaccine administration and/or by SARS-CoV-2 baseline serostatus of the infant's mother. The effect of homologous and heterologous boosters on binding antibodies and neutralizing antibody titers in neonates born to previously vaccinated mothers will be evaluated descriptively by group and overall.

A secondary objective of the study is to assess antibody levels against SARS-CoV-2 in neonates/infants born to adult participants who have received Ad26.COVS during the 2nd and/or 3rd trimester of pregnancy, at birth (ie, in cord blood) and at approximately 2 months and 6 months, of age by group and overall, using ELISA (S-ELISA, EU/mL and GMCs).

A further secondary objective of the study is to assess antibody levels against SARS-CoV-2 in neonates/infants born to adult participants who have received Ad26.COVS during the 2nd and/or 3rd trimester of pregnancy, at birth (ie, in cord blood), as measured by VNA titers (antibody GMTs) by group and overall.

9.2.2. Safety

The primary and secondary objectives of the study are to explore the safety and reactogenicity of Ad26.COVS administered IM as a 1-dose (5×10^{10} vp) schedule, during the 2nd and/or 3rd trimester of pregnancy by group and overall. In addition, safety and reactogenicity of a booster vaccination of Ad26.COVS at 5×10^{10} vp, in eligible, consenting vaccine naïve participants at study entry (Group 4), administered IM not earlier than 2 months after completion of the

participant's Ad26.COV2.S vaccination in the study. Safety will be evaluated by group and overall by monitoring:

- For adult participants, AEs including solicited local and systemic AEs for up to 7 days after vaccination, or until resolution, and unsolicited AEs for 28 days after vaccination, SAEs, and AESIs observed following vaccination will be collected for the whole study duration and up to 12 months postpartum, and MAAEs (including new onset of chronic diseases) up to 6 months post-vaccination or up to 12 months if resulting in study discontinuation; AEs leading to discontinuation (entire study); pregnancy outcomes (including, live term birth, live preterm birth, stillbirth, and abortion).
- Pregnancy-related AEs throughout pregnancy in adult participants (including gestational diabetes, gestational hypertension, premature rupture of membranes, premature labor, premature uterine contractions, poor or restricted fetal growth, pre-eclampsia, eclampsia, vaginal or intrauterine hemorrhage [non-exhaustive]).
- Outcomes in neonates and infants (normal neonate, term neonate with (or without) complications, preterm neonate with (or without) complications, neonatal infection, respiratory distress, congenital anomalies, neonatal death, low birth weight, and small for gestational age from birth until approximately 12 months of age [non-exhaustive]), SAEs (including MIS-C), and AESIs in neonates and infants from birth until end of study (approximately 12 months of age), and MAAEs in neonates/infants from birth until 6 months of age or from birth until discontinuation, if the MAAE is resulting in study discontinuation; AEs leading to discontinuation (entire study).

9.3. Populations for Analysis Sets

For purposes of analysis, the following populations are defined:

Population	Description
Enrolled Adults	All adult participants who sign the ICF
Full Analysis Set-Adults (FAS-A)	All enrolled adult participants with at least one vaccine administration documented
Full Analysis Set-Non-vaccinated Neonates/Infants (FAS-NVN)	All non-vaccinated neonates/infants (NVN) born to Ad26.COV2.S vaccinated adult participants
Per protocol Immunogenicity-Adults (PPI-A)	All vaccinated adult participants for whom immunogenicity data are available excluding adult participants with major protocol deviations that are expected to impact the immunogenicity outcomes. In addition, samples obtained from participants after SARS-CoV-2 infection occurring after baseline (if applicable) will be excluded from the analysis
Per protocol Immunogenicity- Non-vaccinated Neonates/Infants (PPI-NVN)	All non-vaccinated neonates/infants (NVN) born to Ad26.COV2.S vaccinated adult participants for whom immunogenicity data are available excluding neonates/infants born to participants with major protocol deviations that are expected to impact the immunogenicity outcomes (for example missed vaccinations in the mothers), or neonates/infants with major protocol deviations that are expected to impact the immunogenicity outcomes
The list of major protocol deviations to be excluded from the immunogenicity analyses will be specified in the Major Protocol Deviation Criteria document and/or this list will be reported into the protocol deviation dataset of the clinical database before database lock.	

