Per protocol Immunogenicity- Non-vaccinated Neonates/Infants (PPI-NVN)	All NVN born to Ad26.COV2.S vaccinated adult participants for whom immunogenicity data are available excluding neonates/infants born to participants with major protocol deviations that are expected to impact the immunogenicity outcomes (for example missed vaccinations in the mothers), or neonates/infants with major protocol deviations that are expected to impact the immunogenicity outcomes

Population	Description
	The list of major protocol deviations to be excluded from the immunogenicity analyses will be specified in the Major Protocol Deviation Criteria document and/or this list will be reported into the protocol deviation dataset of the clinical database before database lock.

Primary/Secondary Endpoint(s)

Immunogenicity Endpoints

No formal statistical testing of immunogenicity data is planned. Descriptive statistics (geometric mean and confidence intervals, or median and interquartile range Q1-Q3, as appropriate) will be calculated by group and overall, for immunologic parameters for all available time points for adult participants receiving Ad26.COV2.S during the 2nd and/or 3rd trimester of pregnancy.

Descriptive statistics will also be presented for neonates/infants of adult participants who have received Ad26.COV2.S during the 2nd and/or 3rd trimester of pregnancy by group and overall.

Several definitions of serological responses will be applied (fold increases in GMC [S-ELISA] or GMT [VNA]). Graphical representations of immunologic parameters will be prepared as applicable. Frequency tabulations will be calculated for discrete (qualitative) immunologic parameters, as applicable.

The impact of baseline characteristics on the humoral responses may be explored graphically or with descriptive statistics by group and overall.

For adult participants, all immunogenicity analyses will be performed on the PPI-A by group (previous vaccination status) and overall. Immunogenicity analyses may also be performed by stage of pregnancy at which the vaccine was administered, vaccination regimen (ie, 1-dose schedule or 1-dose schedule with a booster dose), SARS-CoV-2 baseline serostatus and by actual vaccine history within each group.

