9.4.1. General Considerations

Analysis populations are defined in Section 9.3.

Primary and final analyses are defined in Sections 9.5.1 and 9.5.2.

No formal statistical testing of safety or immunogenicity data is planned. Safety and immunogenicity will be summarized with descriptive statistics by group and overall. Safety and immunogenicity analyses may also be performed by stage of pregnancy (16-27 weeks, 28-38 weeks), administration of booster (Yes, No), SARS-CoV-2 baseline serostatus (Positive, Negative) at which the vaccine was administered and by actual vaccine history within each group.

For adult participants, all safety analyses will be performed on the FAS-A and immunogenicity analyses will be performed on the PPI-A by group and overall.

For neonates/infants, safety analyses will be performed on the FAS-NVN and immunogenicity analyses will be performed on the PPI-NVN set by group and overall.

The number and percentage of participants screened, enrolled, vaccinated, received a booster vaccine and completed follow-up will be summarized by group and overall.

Baseline is considered as the last available assessment before vaccination. For neonates baseline is value at birth.

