9.4.3. Exploratory Endpoint(s)

Transfer of maternal humoral immunity to the infant will be assessed, including:

- levels of maternal IgA and/or other Ig subtypes against SARS-CoV-2 in colostrum and breast milk within 1 week postpartum and at 6 weeks postpartum (Day 43 PP follow-up visit), respectively, if feasible, in a subset of participants who had received Ad26.COV2.S vaccine during the 2nd and/or 3rd trimester of pregnancy. Levels of maternal IgA and/or other Ig subtypes against SARS-CoV-2 will also be assessed in colostrum and/or breast milk, if feasible, at the time of booster vaccination and 28 days post booster vaccination, in participants who were vaccine naïve at study entry and receive a booster after pregnancy completion.
- levels of antibodies in peripheral blood from adult participants and cord blood at the time of delivery. Serological response as measured ELISA will be assessed using GMCs. The GMR (ratio of immunologic parameters between blood and cord blood at time of delivery) will be calculated together with confidence intervals. Additional characterizations will be described in the SAP.

Cellular immune responses induced in participants during the 2nd and/or 3rd trimester of pregnancy after vaccination with Ad26.COV2.S may be further explored using PBMCs obtained on Day 1 (pre-dose), 28 days after vaccination, and at the time of delivery (if feasible), for a subset of participants. With only 1 participant in this subset at the time of writing this Protocol Amendment 7, PBMC sampling may be removed from the study as of Protocol Amendment 7 approval. Analysis will be described in more detail in the SAP.

The correlation between the binding antibody (ELISA) titers and neutralizing antibody (VNA) titers to SARS-CoV-2 will be assessed at selected timepoints using Spearman's rank correlation. Additional details will be provided in the SAP.

The occurrence and severity of COVID-19 infection (asymptomatic and symptomatic) in adult participants or in neonates/infants of participants who have received Ad26.COV2.S during the 2nd and/or 3rd trimester of pregnancy, will be assessed using the case definitions in outlined in Section 10.8.

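### The infant per-protocol set has no rule for samples taken after maternal or infant SARS-CoV-2 infection, although the adult set has one, so infection antibody can count as vaccine response

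*Protocol*

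**What the plan says.** The Synopsis and Section 9.3 both define two per-protocol immunogenicity sets.

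- **Adults (PPI-A).** Participants with relevant major protocol deviations are left out and, as a separate and additional rule, "samples obtained from participants after SARS-CoV-2 infection occurring after baseline (if applicable) will be excluded from the analysis".
- **Infants (PPI-NVN).** Section 9.3 takes "All non-vaccinated neonates/infants (NVN) born to Ad26.COV2.S vaccinated adult participants for whom immunogenicity data are available excluding neonates/infants born to participants" with major deviations, and also leaves out "neonates/infants with major protocol deviations that are expected to impact the immunogenicity outcomes". The Synopsis has the same construction ("excluding neonates/infants born to participants with major protocol deviations that are expected to impact the immunogenicity outcomes"). Neither place mentions SARS-CoV-2 infection.

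On the deviation list, Section 9.3 says: "The list of major protocol deviations to be excluded from the immunogenicity analyses will be specified in the Major Protocol Deviation Criteria document". It may alternatively be reported in the deviation dataset before lock.

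Section 9.4.1 states for infants that "immunogenicity analyses will be performed on the PPI-NVN set by group and overall", and Section 9.2.1 agrees. The infant secondary endpoints in the Synopsis and Section 3 are S-ELISA in cord blood and at about 2 and 6 months, and VNA in cord blood. Each is labelled a serological response to vaccination. Section 9.2 gives the wider aim as immunity from placental transfer of IgG.

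**The concern.** S-binding and neutralizing antibody rise after infection as well as after vaccination, and nothing in the protocol says that either assay separates the two sources. The sponsor dealt with this for mothers by dropping their post-infection samples. The adjacent definition for infants leaves the same contamination in place by three routes:

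- cord blood from a mother infected after vaccination and before delivery;
- the 2- and 6-month samples of that mother's infant, which carry the same transferred antibody;
- samples from an infant infected after birth.

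The infant analyses may be split by serostatus, but only by the mother's status at baseline (Sections 9.2.1 and 9.4.2). That split cannot detect an infection after vaccination. At stake is whether the infant antibody levels can be read as the vaccine's contribution, which is how the endpoints are labelled.

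**Working it through.** No figure in the protocol depends on this point, so there is none to reproduce. The check is a comparison of text, followed by an illustration of scale.

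**Comparison of text**

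1. PPI-A has two kinds of exclusion: participants with major deviations, and samples after post-baseline infection. The second is introduced as an addition to the first, so the protocol does not itself treat infection as a deviation.
2. PPI-NVN has only the first kind, applied to mother and infant. A deviation list, wherever it is kept, does not by its nature catch an infection.
3. Sections 9.2.1 and 9.4.1 put infant immunogenicity on PPI-NVN. No other section removes cord or infant samples after infection from the secondary infant endpoints.
4. Elsewhere the protocol keeps infection apart. Section 3 has a separate exploratory objective for the infant immune response after infection, and Section 10.4.1 moves adverse events caused by confirmed infection into separate tables.
5. Much of the information needed is already planned: maternal N-serology on Day 1, Day 29, at delivery and at 6 months postpartum (Sections 1.3.1 and 1.3.2), serology within the infant blood sample (Section 1.3.3), and RT-PCR surveillance of both (Sections 1.3.4 and 1.3.5).

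**Illustration of scale**

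Let a fraction f of the retained samples carry antibody raised k-fold by infection, and let g be the geometric mean without infection. Then

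log GMC = (1 − f) log g + f log(k g), so GMC = g × k^f.

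Both f and k are assumptions; the documents give neither. Inflation factors k^f:

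| f | k = 3 | k = 5 | k = 10 | k = 20 |
|---|---|---|---|---|
| 5% | 1.06 | 1.08 | 1.12 | 1.16 |
| 10% | 1.12 | 1.17 | 1.26 | 1.35 |
| 20% | 1.25 | 1.38 | 1.58 | 1.82 |
| 30% | 1.39 | 1.62 | 2.00 | 2.46 |

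Small groups make single cases matter. With k = 10, one affected infant among five gives 10^(1/5) = 1.58, and three among 22 give 10^(3/22) = 1.37. Applying the adult rule to infants returns the factor to 1.00 for the infections that are identified.

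**The case against.** The other side has several good arguments.

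- **The target may be descriptive.** The infant objective is worded as antibody levels in infants of vaccinated mothers, and maternal IgG raised by infection is also transferred across the placenta. Levels regardless of infection are a legitimate summary. This stands in part, and is why the excluded samples belong in a supportive table. It does not fit an endpoint labelled as response to vaccination, or a sponsor that has already chosen the other approach for mothers.
- **Another document may fill the gap.** The SAP or the deviation document could add an exclusion. But the protocol states both definitions explicitly, and a SAP that follows them repeats the difference.
- **The maternal/cord ratio.** A reader might infer that this ratio must compare different mother-infant pairs, because an infected mother's delivery sample is dropped while the cord sample is kept. The text does not establish that. Section 9.4.3 says only "The GMR (ratio of immunologic parameters between blood and cord blood at time of delivery) will be calculated together with confidence intervals"; it names no analysis set and does not say the ratio is unpaired. Computed within pairs, such a dyad drops out. Sections 3 and 9.2.1 also treat cord blood partly as an adult measure, so the adult rule may reach it in this exploratory comparison. What remains is that complete pairs are not stated.
- **Infant fold-rises.** A reader might join "For neonates baseline is value at birth" (Section 9.4.1) to the fold-increase definitions in Section 9.4.2 and conclude that infant responders would be infected infants. Section 9.4.2 does not clearly apply those definitions to infants, the infant objectives in Section 9.2.1 speak of GMCs and GMTs, and assay variation can also produce rises.
- **Severity.** No hypothesis is tested, enrolment has ceased, and Section 9.4 allows some endpoints to be listed only. This stands and lowers the priority.

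**Conclusion.** The gap is real and appears in both statements of the analysis sets. Followed as written, the plan keeps infection-induced antibody in the secondary infant S-ELISA and cord VNA endpoints while removing it from the mothers' results. Where infection raises antibody, the bias is upward. Its size cannot be estimated from the documents: the k^f values show scale only, and the larger ones need both a high infection fraction and a large, uniform boost.

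The conclusion rests on the protocol text alone and assumes that no unseen document adds the missing rule. It does not extend to a claim that the maternal/cord ratio is necessarily mismatched or that fold-rise responder rates are planned for infants. For a descriptive study with enrolment stopped, this is a point that should be fixed, not one that invalidates the plan.

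**What to change.** In the PPI-NVN definition, in both the Synopsis and Section 9.3, add a sample-level rule for the main summary:

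1. Exclude cord and infant samples when the mother had SARS-CoV-2 infection, by molecular test or N-seroconversion, between baseline and delivery.
2. Exclude an infant's samples from the infant's own infection onward. Identify that infection by a molecular test or by a rise in anti-N after birth, not by N-positivity alone: transferred maternal anti-N can make an uninfected infant test positive, and valid samples would be lost.
3. Give a supportive table that includes the excluded samples, so that levels regardless of infection are also reported.
4. State in Section 9.4.3 that the maternal/cord ratio uses complete mother-cord pairs with both samples valid.

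The change is one of wording and uses tests and samples already planned. The cost is fewer infant samples in the main table, which will be felt most in the by-group results. Infections missed by both PCR and serology would remain in the set.
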